## STUDY PROTOCOL

**Type of Study:** Observational longitudinal prospective. The study has approved by etic comity of clinical research of Hospital 12 de octubre de madrid.

**Target population:** Pediatric population undergoing surgery intervention in 12 de octubre hospital.

**Sample:** A convenience sampling will be carried out among the patients undergoing surgical intervention according eligibility criteria.

- **Inclusion criteria:** Children with age from 4 years to 18 years. Undergoing surgery for any surgical specialty. ASA Status (American Society of Anesthesiologist) from I to III.
- **Exclusion Criteria:** Children who do not understand and speak Spanish correctly. Children with verbal communication problems.
- **Stratification of the sample:** The sample will be divided into 2 sample groups: a) children into 4 to 8 years, and b) children into 8 to 18 years.
- **Sample size:** To assess the degree of association between the different clinical variables and the development of chronic postsurgical pain in the pediatric population, the calculation of the sample size was based on previous literature that proposes 20 cases per variable in order to estimate a prediction model in a relatively stable manner. Therefore, taking into account that a total of 13 predictor variables were used (anxiety, catastrophism, fear of pain, fear of movement, pain interference, disability, limitation of activities, prediction of chronic pain in children and

catastrophism, anxiety, fear of pain, fear of movement of parents / guardians / companions), it was considered necessary to include at least 260 children undergoing surgery to meet the objective of this study

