### **Study design.**

- On the day of admission to the pediatric surgery service of the hospital, the potential participant and parents of the study in progress will be informed. First, patients and parents will be informed about the possibility of voluntary participation in the study. Next, the objective, process and potential benefits of this will be reported. The consent of the legal guardians will then be requested. They will be asked to fill in the information of the demographic and clinical variables, answering the self-assessment instruments (the data collection will have an estimated time of 30 'per subject), both children and parents / companions. After the surgical intervention and within a period comprised in the first 5 days, an evaluation of the dependent variables (intensity, location and distribution of pain) will be carried out in both children and parents. They should fill in the self-assessment instruments in the same way as in the pre-surgery session (this will take approximately 10 minutes).
- At 10 days, 3 months, 6 months and 12 months after the intervention, will contact the patients and relatives by telephone, and they will be asked to reply again to the evaluation of all the variables. The evaluation will be carried out by telephone interview.
- The information sheet, the informed consent, and the evaluation instruments will be collected by a researcher, stored and guarded in the Department of Radiology, Rehabilitation and Physiotherapy of the Complutense University of Madrid. Thus, complying with the provisions of Organic Law 3/2018, of December 5, on the Protection of Personal Data and guarantee of digital rights.

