CHRONIC POSTSURGICAL PEDIATRIC PAIN.

TITLE: RISK FACTORS TO DEVELOP CHRONIC POSTSURGICAL PEDIATRIC PAIN

INVESTIGATOR PRINCIPAL: [name]

PROJECT ENTITIES: COMPLUTENSE UNIVERSITY OF MADRID & 12 OCTUBRE PEDIATRIC HOSPITAL.

NUMBER OF IDENTIFICATION: 26/618

DATE: 15TH December 2020.

Statistical Analysis Plan

The results will be analyzed with the SPSS 25 statistical program (SPSS, Inc., Chicago, IL, USA). The interpretation of the statistical tests will be carried out based on a significance level of 5% ($P < 0.05$). First, the demographic variables of the sample will be presented as mean \pm standard deviation (SD), in the case of quantitative variables, and as an absolute value (relative frequency percentage in the case of qualitative variables).

The correlation of the risk factors of both children and parents with chronic postsurgical pain in children will be analyzed. To do this, the Pearson Correlation Coefficient will be used, categorizing the magnitude of the correlation as follows: strong (> 0.60), moderate (0.30-0.60), and weak or very weak (< 0.30).

Additionally, a multiple linear regression model will be used to determine the degree of association between risk factors and chronic postsurgical pain. Specifically, the intensity and location of pain will be included as criterion variables, while catastrophizing, anxiety, fear of pain, fear of movement and quality of life will be considered as predictor variables. The degree of multicollinearity existing between the predictor variables will be evaluated using the Variance Inflation Factor (VIF). The strength of association will be examined using the adjusted coefficient of determination (adjusted R^2). In addition, the regression coefficient (B), the P -value and the standardized beta coefficient (β) will be calculated for each predictor variable of the reduced final model. Thus, it will be possible to determine the variables that most directly influence the regression model.

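### Recruitment is by convenience with no approach order and no log of eligible children not enrolled, so selection that could distort r, standardized beta and adjusted R² can be neither limited nor checked

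*Protocol*

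**What the plan says.** The target population in the protocol is "Pediatric population undergoing surgery intervention in 12 de octubre hospital". On how children are drawn from it, the Sample section says only: "A convenience sampling will be carried out among the patients undergoing surgical intervention according eligibility criteria". Under Study design, families are approached on the day of admission, when "patients and parents will be informed about the possibility of voluntary participation in the study". The questionnaires then go to children and to parents or companions, and "the data collection will have an estimated time of 30 'per subject".

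No section gives an order of approach, a log of eligible, approached and declining families, or a comparison of participants with non-participants.

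The SAP's correlation paragraph sorts each factor by its Pearson coefficient: "strong (> 0.60), moderate (0.30-0.60), and weak or very weak (< 0.30". Its regression paragraph measures strength of association by adjusted R² and reports B, the P-value and standardized beta for each predictor in the reduced final model, so as to identify the most influential variables. Catastrophizing, anxiety, fear of pain and fear of movement are among the predictors.

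**The concern.** With convenience sampling, whoever recruits decides which eligible families to approach, and the families approached may refuse. Either step could plausibly depend on child or parent anxiety, catastrophizing or fear, or on the size and urgency of the operation. The first group are the predictors themselves.

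This matters because of the measures chosen. Pearson's r, standardized beta and R² depend on how widely the predictor varies in the sample as well as on how steeply pain rises with it. If the sample covers a narrower or wider range than the target population, these measures move even when the underlying relation is unchanged. Predictors restricted to different degrees could also change places in a ranking by beta. A factor near a band limit could be graded differently because of who was enrolled, and without a log a reader would have no means of judging whether that was likely.

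**Working it through.** **The plan's own figure.** The Sample size paragraph asks for "20 cases per variable in order to estimate a prediction model in a relatively stable manner" and counts 13 predictors: 20 × 13 = 260, which reproduces. This fixes how many children are recruited, not which ones. No approach rate or refusal rate is given, so every selection scenario below is an assumption.

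**Formula.** Let u be the SD of the predictor in the sample divided by its SD among all eligible families. If selection acts on the predictor alone and the relation is linear with constant residual spread,

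r′ = u·r / √(1 − r² + u²·r²).

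With one predictor, beta = r′ and R² = r′². B does not change.

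**Complete loss of the top fraction q (normal scores).** With c the (1 − q) normal quantile and λ = φ(c)/Φ(c), u² = 1 − cλ − λ². For q = 0.30: c = 0.524, λ = 0.348/0.70 = 0.497, u² = 1 − 0.260 − 0.247 = 0.493, u = 0.702. Then r′ = 0.40 × 0.702 / √(0.84 + 0.16 × 0.493) = 0.281/0.959 = 0.293.

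**Graded loss.** The log-odds of non-enrolment rise linearly with anxiety, by an assumed odds ratio (OR) per SD. The intercept is set so that 30% or 40% are not enrolled, and u is found by numerical integration over the normal distribution. For 30% and OR 5: u = 0.869, so r′ = 0.40 × 0.869 / √(0.84 + 0.16 × 0.755) = 0.348/0.980 = 0.355.

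Results for a true r of 0.40 (R² = 0.16):

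| Assumed pattern of loss | r′ | SAP band |
|---|---|---|
| Unrelated to the predictor | 0.40 | moderate |
| 30% lost, OR 2 / 3 / 5 per SD | 0.386 / 0.372 / 0.355 | moderate |
| 40% lost, OR 2 / 3 / 5 per SD | 0.384 / 0.367 / 0.348 | moderate |
| Half of the top 30% lost | 0.37 | moderate |
| All of the top 10% / 20% lost | 0.346 / 0.316 | moderate |
| All of the top 30% / 40% lost | 0.293 / 0.273 | weak or very weak |
| Middle 20% / 30% lost | 0.44 / 0.46 | moderate (r rises) |

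**When the band changes.** Setting r′ = 0.30 with r = 0.40 gives u² = 0.0756/0.1456 = 0.519, so u = 0.72. The sample SD would have to fall by more than a quarter. The graded scenarios leave u between 0.85 and 0.96. For a true r close to a limit, less is needed: 0.35 falls to 0.274 if all of the top 20% are lost, and 0.65 falls to 0.585 if all of the top 10% are lost.

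**The slope.** In a simulation of 2,000,000 draws, B stayed at 0.40 when the top 20% on the predictor were removed. When the top 20% on the outcome were removed instead, B fell to 0.25 and r to 0.316. Future pain cannot itself drive enrolment, but operation size or urgency might partly stand in for it. B is therefore protected only if selection acts on the predictor alone.

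**Sampling error for scale.** At n = 260 and r = 0.40, Fisher's z = 0.424 with half-width 1.96/√257 = 0.122, which gives a 95% interval of about 0.29 to 0.50.

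**The case against.** The strongest reply is that this is a general limitation, openly declared, in a single-centre observational study, and that its effect here may be small. Much of that stands. Convenience sampling by researcher availability may be unrelated to anxiety, in which case r does not move. Worried families might be keener to join a pain study. The realistic graded scenarios shift r by 0.05 or less, well inside the sampling interval. B is reported as well. What remains is that selection bias, unlike sampling error, does not shrink with more children and is not reflected in a P-value, and that the SAP's bands rest on r rather than B.

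A reader might infer that the most anxious families will be missed on a stressful admission day and that moderate factors will therefore be graded weak. The documents do not support this. They give no refusal pattern and do not call the day stressful, and the Ethical Aspects section judges the 30 minutes acceptable for families. The drop in band from 0.40 requires total, one-sided loss of at least 30% of families, and loss from the middle of the range would raise r.

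It can also be objected that nothing in the documents shows every eligible family can be approached. That is correct: they give no caseload or staffing. With 30 minutes per subject, several eligible admissions on one day may exceed what one researcher can do. The remedy has to allow for children who are eligible but not approached.

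**Conclusion.** The point holds as a weakness of design and reporting, not as a demonstrated bias. The protocol leaves selection to recruiter choice and refusal and plans no record that would let anyone assess it, while three of the SAP's reported measures depend on predictor spread. Direction and size are unknown. With a true r of 0.40, normal scores and selection on the predictor alone, graded loss of 30-40% gives about 0.35-0.39, and a change of band needs complete loss of the most anxious 30% or more. True values close to 0.30 or 0.60 are more exposed. The change is worth making because it is cheap and must be made prospectively: families who were never approached cannot be reliably reconstructed after recruitment closes.

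**What to change.** In the Sample section, replace convenience sampling by consecutive approach: on the days the researcher already attends, eligible children are approached in order of admission. Keep an anonymous log of eligible children not enrolled, with age group, sex, surgical specialty, elective or urgent, not approached or declined, and reason. In the SAP, add that the enrolled share will be reported and that enrolled and non-enrolled children will be compared on the logged items.

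This removes selection by recruiter choice on those days, makes refusals visible and allows a check on case mix. It does not enrol families who refuse, does not cover children admitted on other days, and does not show directly whether the range of anxiety was restricted, because anxiety is not measured in those not enrolled. The report should say so and should not rest conclusions on the r bands alone where B is available.

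The cost is a sentence or two in each document, a short log entry per child and possibly slower accrual. The target of 260 and the planned tests do not change.

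### Children from every surgical specialty are pooled and no model contains a term for the operation, so surgical case mix can pass for a psychological risk factor

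*Protocol*

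**What the plan says.** **Who enters.** The protocol's inclusion criteria admit children "Undergoing surgery for any surgical specialty. ASA Status (American Society of Anesthesiologist) from I to III". Sampling is by convenience. The exclusions concern only language and communication: "Children who do not understand and speak Spanish correctly. Children with verbal communication problems". Nothing restricts the procedure, its size or its urgency.

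**How the sample is divided.** By age only: "The sample will be divided into 2 sample groups: a) children into 4 to 8 years, and b) children into 8 to 18 years".

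**What is collected.** On the day of admission, families complete the self-assessment instruments. Under Study design, "They will be asked to fill in the information of the demographic and clinical variables"; these variables are not listed.

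**What is analysed.** The SAP plans Pearson correlations of child and parent risk factors with chronic pain. It then plans a multiple linear regression with pain intensity and location as outcomes, in which "catastrophizing, anxiety, fear of pain, fear of movement and quality of life will be considered as predictor variables". It reports coefficients from a reduced final model. It describes no partial correlation and no covariate, subgroup or sensitivity analysis by surgery.

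**Sample size.** The protocol applies a rule that "proposes 20 cases per variable in order to estimate a prediction model in a relatively stable manner" to 13 predictors. It names 12, of which eight are listed first and four belong to parents or companions. None of the 12 is surgical, and the thirteenth is not named.

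**The concern.** The operation is normally decided before the admission questionnaires are filled in. It may influence the answers, because a child or parent facing a larger procedure may be more anxious or fearful. It may also influence pain months later. If both hold, the operation is a common cause of score and outcome, and an analysis without it mixes two explanations: anxious children develop pain, or children having larger operations are both more anxious and in more pain.

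The study's title and objective concern risk factors for chronic postsurgical pain, so this is the distinction its conclusion needs. Convenience sampling adds to the problem, because the size of the reported associations would depend partly on which procedures happened to be recruited. Adjusting the psychological scores for one another does not stand in for adjusting for the operation.

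**Working it through.** **1. The plan's own figure.** 20 cases per variable × 13 predictors = 260, as stated. The 12 named predictors would give 20 × 12 = 240.

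**2. Inputs.** From the documents: n = 260 and a 5% significance level, taken as two-sided because sidedness is not stated. Assumed, because the documents do not give them:
- a, the correlation of operation size with the psychological score;
- b, the correlation of operation size with later pain;
- no effect of the score on pain in its own right.

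**3. Raw Pearson correlation.** The induced correlation is r = a × b. The rejection probability by Fisher's z is Φ(z − 1.96) + Φ(−z − 1.96), with z = atanh(ab) × √257.

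| a / b | induced r | z | significant |
|---|---|---|---|
| 0.1 / 0.2 | 0.02 | 0.32 | 6% |
| 0.2 / 0.2 | 0.04 | 0.64 | 10% |
| 0.2 / 0.3 | 0.06 | 0.96 | 16% |
| 0.3 / 0.4 | 0.12 | 1.93 | 49% |
| 0.4 / 0.4 | 0.16 | 2.59 | 74% |

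At n = 260 any correlation beyond about ±0.12 is significant. A simulation (4,000 runs per setting) gave 9% at 0.2/0.2 and 74% at 0.4/0.4 without adjustment. With operation size in the model, the rate was about 5% in both.

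**4. Five-predictor regression.** Suppose each of the five constructs correlates a with operation size and ρ with each of the others, with ρ from 0.3 to 0.6 (assumed). Then, on standardised variables:
- each coefficient is ab / (1 + 4ρ);
- R² = 5(ab)² / (1 + 4ρ);
- VIF = (1 + 3ρ) / [(1 − ρ)(1 + 4ρ)];
- the t-test has noncentrality coefficient / √[(1 − R²) × VIF / 260].

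Example for a = b = 0.4, ρ = 0.3: coefficient 0.16 / 2.2 = 0.073; R² = 5 × 0.0256 / 2.2 = 0.058; VIF = 1.9 / (0.7 × 2.2) = 1.23; noncentrality 1.09; rejection 19%.

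| a / b | per coefficient, ρ = 0.6 to 0.3 | overall F test, ρ = 0.6 to 0.3 |
|---|---|---|
| 0.2 / 0.3 | 5-7% | 12-16% |
| 0.3 / 0.4 | 7-13% | 40-60% |
| 0.4 / 0.4 | 8-19% | 67-88% |

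These rates are for the full model. Selection down to a reduced model could raise the per-coefficient rates.

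**5. Cost of adjusting.** Operation size in three categories takes 2 degrees of freedom, urgency 1 and ASA class I-III 2, a total of 5. Added to the stated 13 predictors: 260 / 18 = 14.4 cases per variable. Added to the SAP's five constructs as single terms: 260 / 10 = 26. If four of those constructs are entered for both child and parent, plus one quality-of-life score (one possible reading), the count is 9 + 5 = 14 and 260 / 14 = 18.6. Without the urgency term it is 260 / 13 = 20.

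**The case against.** **Prediction needs no causal adjustment.** The sample-size text speaks of degree of association and of a prediction model. For pure prediction, a score that tracks operation size is a genuine marginal predictor, and rejecting r = 0 is then no error. This stands in part, because the documents mix the two aims. But the SAP wants to identify which variables act most directly in the model, and the ethics section appeals to the mechanisms of chronic pain. Those are explanatory aims. Even for prediction, the plan leaves out a variable that is available at baseline.

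**Surgery may be in the data.** The clinical variables are unlisted and the thirteenth predictor is unnamed, so the operation may well be recorded. That is fair, but recording a variable does not adjust for it, and the SAP's explicit predictor list omits it.

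**The common cause is not documented.** Correct. Neither link is stated or quantified in the documents, and weak links do little harm.

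**Broad eligibility is a legitimate choice.** Agreed. The defect lies in the analysis, not in admitting all specialties.

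Three stronger readings are tempting but unsupported:
- *Emergency operations drive the bias.* The documents never mention them. They are only not excluded, and same-day consent with about 30 minutes of questionnaires before surgery would tend to limit them.
- *The 49% and 74% figures apply to the regression.* They describe only the raw correlation.
- *Case mix could reverse the sign of a coefficient.* The mechanism is positive on both arms, and no calculation here shows a reversal.

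**Conclusion.** The point holds as a gap in the SAP. All specialties are pooled, age is the only stratifier, and neither planned analysis has a surgical term. That much is certain from the text.

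The size of the bias is not certain. For the raw Pearson test it runs from negligible (6% against a nominal 5%) to severe (74%) over assumed correlations from 0.1/0.2 to 0.4/0.4. For single regression coefficients it is about 5-19% from 0.2/0.3 to 0.4/0.4, while the overall F test rejects in about 12-88% and R² is inflated. All of this assumes that the score has no effect of its own and that larger operations raise both score and pain. The correction is cheap and should be made before the data are analysed.

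**What to change.** In the SAP:
1. Prespecify a small set of surgical covariates taken from the surgical record: operation size in a few categories, and urgency if non-elective cases are enrolled. Add ASA class, which is already needed for eligibility.
2. Keep these terms in every model, including the reduced final model, regardless of P.
3. Report partial correlations adjusted for them beside the raw Pearson coefficients.
4. Base conclusions about risk factors on the adjusted estimates.

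**Cost.** SAP wording and one or two fields from the surgical record, with no extra visits. The model gives up as many as about 5 degrees of freedom. The sponsor should state the final predictor count and the resulting cases per variable: 14.4 if all five terms are added to the stated 13 predictors, and roughly 19 to 26 if the model keeps to the SAP's shorter list. Taken literally, the 20-per-variable rule with 18 terms would ask for 20 × 18 = 360 children. Restating the count, preferably on the shorter list, is the proportionate response rather than enrolling more.

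### Age and the protocol's two age groups have no role in the SAP's correlations or regression, so the risk-factor coefficients may partly reflect age

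*Protocol*

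**What the plan says.** **Protocol, Study Protocol section.** The inclusion criterion is "Children with age from 4 years to 18 years". Recruitment is not random: "A convenience sampling will be carried out among the patients undergoing surgical intervention". Under the stratification bullet the sample is split into "a) children into 4 to 8 years, and b) children into 8 to 18 years". No number per group and no analytic purpose is given, and age 8 appears in both groups. The sample-size bullet names eight child and four parent predictors; age is not among them.

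**SAP.** On demographics it says only that "the demographic variables of the sample will be presented as mean" with SD, or as counts and percentages. It then plans Pearson correlations of child and parent risk factors with pain, graded in bands that include "moderate (0.30-0.60), and weak or very weak (< 0.30". A multiple linear regression follows, in which "catastrophizing, anxiety, fear of pain, fear of movement and quality of life will be considered as predictor variables". B, P and beta are reported "for each predictor variable of the reduced final model", so as to "determine the variables that most directly influence the regression model". Age, age group, strata and covariate adjustment are not mentioned.

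**The concern.** The protocol treats age as important enough to stratify on, and the SAP then makes no use of it in any association analysis. Nothing is randomised and the ages span 14 years. Age is fixed before both the questionnaire scores and the pain, so it can be a common source of both. If it is, part of each coefficient belongs to age, and a ranking of variables by beta or P could credit a questionnaire score with what is really a difference between younger and older children. The Pearson correlations would carry the same component.

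A second gap follows from the first. Neither document says whether the two groups are pooled or analysed separately. If separately, a child aged 8 has no defined model.

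**Working it through.** **1. The plan's own figure.** The protocol's rule is 20 cases per variable with 13 variables: 20 x 13 = 260, which reproduces. The predictors actually named number 8 + 4 = 12 (12 x 20 = 240). Age is in neither this list nor the SAP's five.

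**2. Illustration of size (assumptions, not document figures).** Let a be the correlation of age with each of five predictors and with pain intensity, and let r be the correlation between predictors given age. There is no association between predictors and pain beyond age. All 260 children are analysed together and tested two-sided at 5%.

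- Correlation between predictors: c = a² + (1 − a²)r
- Expected coefficient without age in the model: b = a² / (1 + 4c)
- R² = 5a⁴ / (1 + 4c)
- Variance factor: v = (1 + 3c) / [(1 − c)(1 + 4c)]
- Residual df = 260 − 5 − 1 = 254
- Noncentrality: d = b√254 / √[(1 − R²)v]; the rate comes from the noncentral t distribution

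Worked at a = 0.3:
- r = 0: c = 0.09; b = 0.09/1.36 = 0.066; R² = 0.030; v = 1.026; d = 1.06; rate 18%.
- r = 0.4: c = 0.454; b = 0.09/2.816 = 0.032; R² = 0.014; v = 1.536; d = 0.41; rate 7%.

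Percentage of studies in which a given coefficient is significant:

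| Age correlation a | 0.1 | 0.2 | 0.3 | 0.4 | 0.5 |
|---|---|---|---|---|---|
| n = 260, r = 0 | 5 | 9 | 18 | 34 | 52 |
| n = 260, r = 0.4 | 5 | 5 | 7 | 10 | 16 |
| n = 182 (assumed 30% loss), r = 0 | – | – | 14 | 25 | 38 |
| n = 182, r = 0.4 | – | – | 6 | 9 | 13 |

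**3. What different handling of age does (simulation, same model, a = 0.3/0.4/0.5).**
- Age in years entered: about 5% throughout.
- Only the two-level group entered (4–7 v 8–18, even ages): about 8/14–15/24–26% with r = 0, and 5–6/6/8% with r = 0.4.
- Separate models by group, even ages: the older group has 167 to 191 children (260 x 9/14 to 260 x 11/15, depending on the split and the top age). Its rates are 7–9/11–15/18–25% with r = 0, and 5–6/6–7/7–9% with r = 0.4. The younger group stays at 5–6%.

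**4. Pearson correlations.** The expected correlation is a². For a = 0.1 to 0.5 this is 0.01, 0.04, 0.09, 0.16 and 0.25. By Fisher's z with n = 260, these are significant in about 5, 10, 30, 73 and 98% of studies. At 0.25, about 19% of studies would show a value above the SAP's 0.30 threshold. Adding age to the regression leaves these correlations unchanged.

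**5. Age 8.** With ages evenly spread, 260/15 = 17.3 to 260/14 = 18.6, so about 17 to 19 children belong to both groups as written.

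**The case against.** - **Age is not wholly absent.** It would presumably be summarised with the demographic variables. This stands, so the point is confined to the correlations and the regression.
- **The groups may be meant for separate analysis.** The SAP's silence does not cancel the protocol's split, and the single total of 260 is thin evidence for pooling because the 20-per-variable rule does not address groups. This stands in part. Analysis by group removes some of the age effect, and nearly all of it when the predictors are correlated. It still leaves a span of about ten years in the older group.
- **The large rates are not the plan's rates.** A reader might infer that up to half of the coefficients will be spuriously significant. The documents do not support that: they contain no age correlations, and 52% needs correlations of 0.5 and predictors independent given age. The SAP plans a VIF check, so it expects that predictors may overlap. There is also no stated reason why parents' scores should follow the child's age as closely as the child's own scores.
- **An unadjusted Pearson correlation is not wrong.** A reader might call a value of 0.25 that arises through age, or its label in the SAP's bands, false. It is the true marginal correlation in this model, and values above 0.30 are sampling variation around it. The difficulty is only in reading it as independent of age.
- **The protocol mentions a prediction model.** For prediction alone, leaving age out is not a bias. The SAP, however, sets out to measure association and to rank the variables, so this does not dispose of the point.

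**Conclusion.** The omission is certain from the text. Its consequence is plausible but unquantified: neither its size nor its direction can be taken from the documents. The illustration assumes equal, linear age correlations, no true association and pooled analysis. With a residual correlation of 0.4, the rates stay near nominal up to an age correlation of 0.3; with independent predictors they rise materially from 0.3 upward. A reader might infer that the regression results will be invalid, and the documents do not support that. They support a narrower conclusion: as planned, the coefficients cannot be read as independent of age, and this is avoidable at almost no cost, so the SAP should be changed. The overlap at age 8 is a small defect under pooled analysis, but under analysis by group it decides which model a child enters.

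**What to change.** Add to the SAP, for example: *Age in years at the pre-surgery assessment is entered as a covariate in each regression and is kept in the reduced final model whatever its P value. Pearson correlations are labelled as unadjusted for age, and correlations partialled for age are reported beside them.* Age in years is preferable to the two-level group, which removes only part of the effect. Keeping it in matters because the SAP reports a reduced model, from which it could otherwise be dropped.

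Also state whether the two protocol groups are analysed pooled or separately, and for what purpose, and define them in completed years without overlap at age 8. The boundary is the sponsor's choice.

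**Cost.** No new data: age is an eligibility criterion, and demographic information is collected before surgery. One degree of freedom per model: residual 254 becomes 260 − 6 − 1 = 253. Under the protocol's rule, the 12 named predictors plus age give 13 x 20 = 260, unchanged; the SAP's five plus age give 6 x 20 = 120; only adding age to the stated count of 13 gives 14 x 20 = 280. A linear age term may leave some age effect if the relation is curved.
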